4.1 Summary of study design

Figure 1. SCALE-C study schema

This study will be conducted as an interventional cohort study. A total of 286 people with or at risk of HCV infection will be enrolled from AHS and partnering health services. Individuals at risk of HCV infection are defined by self-reported injecting drug use, incarceration or receipt of opioid substitution therapy within 12 months of screening.

Participants will receive a community-based "test and treat" intervention integrating point-of-care HCV testing, non-invasive liver fibrosis assessment (Fibroscan or APRI) and linkage to care as a strategy to increase HCV diagnosis and testing, enhance scale-up of DAA therapy and reduce HCV prevalence and incidence (Figure 1).

The "test and treat" intervention will consist of:

- Point-of-care HCV testing (anti-HCV Ab or HCV RNA)
 - Choice of initial test will be based on a short HCV risk assessment at enrolment (Figure 2)
- Non-invasive liver fibrosis assessment (Fibroscan[®] or APRI)
- Linkage to care (with medical or nursing assessment), including education regarding HCV transmission and harm reduction
- Immediate DAA initiation (if indicated and clinically appropriate)

Recruitment into the SCALE-C cohort will remain open throughout the study period. Enrolment may occur in concert with standard of care healthcare provision (following written informed consent).

To enhance recruitment and follow up targeted periods of recruitment will be developed in partnership with the participating AHS. Models of recruitment will be provided to AHS for consideration to drive recruitment. Ultimately AHS will determine appropriate models of recruitment to match their target population.

The study consists of screening, HCV treatment (8-12 weeks) if appropriate, and follow-up (up to three years post enrolment). Treated participants will transition into the HCV RNA negative at-risk cohort to assess for incident infection (reinfection) after viral cure (SVR12).

Figure 2. HCV risk assessment at screening and testing pathway

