9.8 Future use of biological samples

After the samples have been analysed for the study endpoints as specified in the protocol, remaining samples will be stored for use in future Human Research Ethics Committee approved hepatitis C related research. Additional consent will be sought for permission to store any remaining DBS samples after sample analyses for study endpoints for future hepatitis C related research. As part of the informed consent process and form, participants will indicate their choice using tick boxes to the storage of remaining samples for use in hepatitis C related future research. Samples from participants who indicate they do not wish for their samples to be used in future research, will be destroyed, or returned to participates if indicated, following sample analyses for study endpoints

10. Statistics

Statistical Analyses and Sample Size Calculations

Primary endpoint: The primary endpoint for the HCV treatment as prevention evaluation is HCV prevalence following implementation of the community-based "test and treat" model.

Secondary endpoints include:

- HCV incidence;
- DAA uptake: Proportion with HCV infection initiating DAA therapy;
- DAA treatment outcome: Proportion who initiated DAA therapy and achieved SVR (defined as HCV RNA below the lower limit of quantitation at post treatment week 12);
- DAA treatment completion: Proportion who completed prescribed treatment course;
- Adherence;
- Reinfection incidence post treatment.

The impact of rapid DAA treatment scale-up on HCV incidence and prevalence

Hypothesis: Rapid DAA scale-up will reduce HCV prevalence by >50%

Outcome: Prevalence of HCV infection

Statistical analysis: The proportion of people with current HCV infection (HCV RNA positive) will be calculated by study period. Confidence intervals for proportions will be calculated.

Sample Size: With enrolment of 370 participants (estimated HCV RNA prevalence in Year One, 35%; alpha=0.05; loss to follow up, 30%), the study has 90% power to detect a relative reduction in HCV RNA prevalence of 50% from the initial to the later study period following scale-up of testing and treatment.

Hypothesis: Rapid DAA scale-up will reduce HCV incidence by >50%

Outcome: Incidence of HCV infection

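### The primary analysis gives a prevalence per study period but never estimates the hypothesised fall, and with open recruitment the later figure depends on when people join

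*Protocol*

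**What the plan says.** Section 10 (Statistics) defines the primary endpoint as "HCV prevalence following implementation of the community-based" test-and-treat model. The hypothesis is "Rapid DAA scale-up will reduce HCV prevalence by >50" per cent. The sample size paragraph enrols 370 people (35% prevalence in Year One, alpha 0.05, 30% loss to follow-up) and says "the study has 90% power to detect a relative reduction in HCV RNA prevalence of 50% from the initial to the later study period". The analysis itself is two sentences: "The proportion of people with current HCV infection (HCV RNA positive) will be calculated by study period. Confidence intervals for proportions will be calculated".

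Four features of the design bear on this:

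- Section 4.1: "Recruitment into the SCALE-C cohort will remain open throughout the study period". Treated participants stay in the cohort as RNA-negative, at-risk members.
- Section 3.2: a person enters the cohort either by being RNA positive at screening or by recent risk.
- Section 4.2 and Schedule of Assessments A: every cohort member has an RNA test about every six months for up to three years.
- Section 2.2: the primary objective concerns prevalence among people attending the participating and partnering services.

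The initial and later periods are given no dates. Nothing says whether the first test of someone who joins late counts in the later proportion.

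**The concern.** The hypothesis and the power statement are about a change between two periods. The method produces two separate proportions, each with its own interval, and no estimate of the change.

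The two proportions also do not come from a fixed set of people. Some contributors are the same individuals retested, many after treatment. Others may be new entrants whose first test precedes any treatment in this study. The mix depends on when sites recruit, which the protocol leaves open. The same treatment success could then appear as a fall above or below 50%. That matters because 50% is the threshold in the primary hypothesis.

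**Working it through.** **Step 1. Reproduce 370.** Inputs from Section 10: 35% initially, 17.5% later (50% relative reduction), 90% power, alpha 0.05 (two-sided assumed, since sidedness is not stated), 30% loss.

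- Arcsine formula for two independent groups: h = 2·asin(√0.35) − 2·asin(√0.175) = 0.403. Then n = 2(1.960 + 1.282)²/h² = 129.5 per period, 259 in total, and 259/0.7 = 370.
- The pooled normal formula gives 131 per period, and 262/0.7 = 375.
- With continuity correction: 142 per period, 284 in total. Multiplying by 1.3 gives 369.2, which rounds up to 370. Dividing by 0.7 gives 406.

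Both routes to 370 treat the periods as two separate groups of people.

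**Step 2. Compare with the design.** If the 259 retained people are tested in both periods, each period has 259 people and not about 130. Even an unpaired comparison of 259 with 259 has 99.6% power, so the stated 90% does not describe the cohort as designed.

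**Step 3. Effect of entrants.** Let f be the share of the later proportion made up of entrants' first tests. The protocol gives no value, so f is assumed. Entrant prevalence is taken as 35%. Section 3.1 gives that figure for drug treatment and harm reduction clients. Over all expected cohort-eligible people it gives (15 + 105)/(15 + 15 + 105 + 195) = 120/330 = 36%.

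Later prevalence = (1 − f) × continuing prevalence + f × 0.35. Apparent fall = 1 − later prevalence/0.35.

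| Entrant share f | Continuing at 17.5%: later prevalence | Apparent fall | Continuing at 10% (assumed): later prevalence | Apparent fall |
|---|---|---|---|---|
| 0% | 17.5% | 50% | 10% | 71% |
| 10% | 19.3% | 45% | 12.5% | 64% |
| 25% | 21.9% | 37.5% | 16.3% | 54% |
| 50% | 26.3% | 25% | 22.5% | 36% |

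The bias can reverse. With no change in continuing members (35%) and 25% entrants at an assumed 10%, later prevalence is 0.75 × 0.35 + 0.25 × 0.10 = 28.75%, an apparent fall of 18%.

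**Step 4. Effect of pairing.** Let p01 be the share going from negative to positive (not given, so assumed), with p10 = 0.175 + p01.

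- Variance of the change per pair: p10 + p01 − 0.175².
- Unpaired variance: 0.35 × 0.65 + 0.175 × 0.825 = 0.372.
- Pairs needed (McNemar): n = [1.960√(p10 + p01) + 1.282√(p10 + p01 − 0.175²)]²/0.175².
- The last column uses 200 retained pairs, which is 70% of the 286 enrolled in Sections 3.1 and 4.1.

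| Newly positive p01 | Paired SE / unpaired SE | Pairs for 90% power | Power with 200 pairs |
|---|---|---|---|
| 0% | 0.62 | 56 | >99.9% |
| 2% | 0.70 | 70 | >99.9% |
| 5% | 0.81 | 91 | 99.8% |
| 8.75% | 0.93 | 116 | 99.0% |
| 11.4% (zero correlation) | 1.00 | 134 | 97.8% |

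The range is reasonable against the plan's own figures. Section 10 expects 29 incident infections with 25% clearing, and 29 × 0.75 ≈ 22. Even if all 22 fell among 200 retained people and none was treated, that is 11%.

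**The case against.** **The contrast is plainly intended, and its model could sit in the SAP.** This is partly right. The choice of model and covariates is SAP detail, and only the protocol was available. But the protocol is not silent: it names a method, and that method followed as written yields no estimate of the fall.

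**The target is prevalence among attendees, so untreated newcomers belong in it.** This has force. Section 2.2 supports it, and a purely within-person result partly restates treatment uptake multiplied by SVR, both already secondary endpoints. It does not rescue the pooled figure, because entry requires RNA positivity or recent risk. Pooled cohort prevalence is therefore not attendee prevalence either.

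**Independent groups are inferred.** True: no sentence says that the periods are different people. The inference rests on how 370 arises, although both routes to it share that assumption.

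**The entrant shares are hypothetical.** Also true. The 50% case fits poorly with the synopsis: 715 person-years over 286 people is 2.5 years each, which implies mostly early enrolment if the study runs three years. Entrants might also be treated and retested within the later period, which would reduce the dilution.

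**Stronger readings that a reader might infer.** One is that the confidence intervals are wrong. They are not: an interval for one period's proportion is valid for that proportion, and no interval for the change is given. Another is that ignoring pairing inflates type I error. With positive within-person correlation it does the opposite. A third is that the effect will be understated. Step 3 shows that the direction is not fixed.

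**Conclusion.** The point holds at moderate severity. The primary hypothesis and power concern a fall of more than 50% between periods, but the stated analysis does not estimate that fall. The later proportion depends on an unspecified mix of retested members and new entrants.

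Under the plan's own 35% to 17.5% scenario with entrants at 35%, shares of 10% to 50% reduce an actual 50% fall to between 45% and 25%. The shares are assumptions, and entrants with lower prevalence would bias the other way.

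The independent-groups basis of 370 does not match a repeatedly tested cohort, but the error is on the safe side. For assumed new positives of 3% to 10%, an unpaired standard error of the change is too large by 35% to 4%. With 200 retained pairs, power is about 98% or more for up to about 11% newly positive. The documents do not support a claim of invalid intervals, of false-positive risk from ignoring the pairing, or of too few participants for the paired contrast.

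**What to change.** 1. Define the initial and later periods, by date or by time since enrolment, and say which tests count in each.
2. State the primary result as a prevalence ratio or difference between the periods with a 95% CI, from a model clustered on participant (for example GEE). Make the primary contrast in participants tested at entry and again at follow-up.
3. Report entrants' first-test prevalence by calendar period separately, as the evidence on attendee prevalence, noting the entry criteria.
4. Restate the power for repeated measurements on the same people, giving the assumed share newly positive and its range.

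The cost is revised wording and one recalculation, with no extra visits or data. The downside is that the headline then describes change within the enrolled cohort, so attendee prevalence should be reported alongside it to keep the link to the objective in Section 2.2.

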Participants with *current HCV infection* (HCV RNA positive) and/or participants who report being *at risk of HCV infection* (HCV RNA negative; history of injecting drug use, history of incarceration, receipt of opioid substitution therapy with 12 months of screening) will undergo the following assessments:

- Point-of-care HCV RNA (if not performed previously)
- Point-of-care HIV and HBV serology
- Collection of dried blood spot (DBS) sample (research sample)
- Screening behavioural questionnaire
- Health outcomes survey (EQ-5D-5L)
- Education regarding HCV transmission and risk reduction

Baseline visit (Point-of-care HCV RNA positive participants only)

Assessment for DAA initiation

This can, and should (if possible), be conducted on the day of the screening (or follow up) visit.

• Clinical assessment with a study nurse

If clinically indicated, the following standard-of-care blood tests will be collected:

- o Phlebotomy for liver function tests, full blood count, biochemistry
- o HCV genotyping via local laboratory
- o HCV RNA (quantitative or qualitative) via local laboratory
- Pregnancy test (for women of childbearing potential only)
- Initiation of pan-genotypic DAA therapy (glecaprevir/pibrentasvir or sofosbuvir/velpatasvir) following discussion with an experienced clinician (face-to-face or remote), if appropriate

Point-of-care HCV RNA positive participants assessed as suitable and willing for treatment will be prescribed eight weeks glevaprevir/pibrentasvir or 12 weeks sofosbuvir/velpatasvir under PBS S85 (dispensed as a 4-week supply). The time of the first dose of therapy will be recorded.

Participants not deemed suitable for treatment under this simplified community-based model of care will be referred for specialist follow-up.

For point-of-care HCV RNA positive participants who decline DAA treatment, site study staff will discuss with the participant the reasons for not initiating DAA treatment. These participants may remain in the cohort and will be followed longitudinally. They will also be approached for involvement in the qualitative study.

On-Treatment and Post-Treatment Phase (For participants who initiate DAA treatment)

On-Treatment Week 4 and Week 8

The following procedures will occur at Week 4 and Week 8 on-treatment:

- Clinical assessment with nurse (as required)
 - Clinical assessment will be conducted on an as-needed basis at discretion of the participant and/or the nurse.

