9.1 Laboratory supplies and sample processing

Laboratory supplies for collection of research specimens (DBS) will be supplied by the Kirby Institute.

A DBS sample will be collected at the time points specified in the Schedule of Assessments. Samples will be collected by sites, dried (4 hours minimum but preferably overnight) and then posted to the Kirby Institute laboratory within 1 week of collection for storage at -80°C.

DBS samples will be used for study endpoint analysis. HCV RNA will be measured using in-house and commercial assays. Sequencing of the viral genome will also be performed as a more accurate means of genotyping. Data generated from the sequencing may also be used to distinguish relapse from reinfection, to examine the prevalence of mixed infection, to look at clusters and networks in communities and factors associated with relapse including resistance-associated substitutions (RAS) and to perform phylogenetic analyses to examine molecular epidemiology. For HCV phylogenetic analysis, only viral RNA is extracted, amplified and sequenced. No human genomic analysis is being proposed. There is no potential to identify human genetic traits.

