9.7 HCV RNA Recurrence

Among people with an end of treatment response, participants with HCV RNA recurrence (detectable HCV RNA) will be identified. HCV sequencing will be performed from dried blood samples using Core-E2, NS5A or NS5B Sanger sequencing (23). HCV reinfection will be defined by the detection of infection with a strain distinct from the primary infecting strain based on defined genetic distance-based cut-offs and phylogenetic tree construction for reinfection and relapse developed by the investigators (23).

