Statistical analysis: HCV incidence will be calculated using person-time of observation. The estimated date of infection will be calculated as the midpoint between the dates of the last undetectable HCV RNA test (or end of treatment) and the first detectable HCV RNA test at the time of HCV infection. Time at risk will commence at the date of first undetectable HCV RNA (or end of treatment), and end at the estimated date of infection, death, loss-to-follow up or end of study. Confidence intervals for rates will be calculated using a Poisson distribution. Poisson regression analysis (or another time-to-event analysis) will be used to estimate crude and adjusted incidence rate ratios (IRR) and corresponding 95% CI to evaluate factors associated with incident infection.

Uptake of DAA therapy among people with HCV infection attending Aboriginal Medical Services

Hypothesis: A community-based "test and treat" intervention integrating point-of-care HCV testing will lead to increased HCV treatment uptake among people attending Aboriginal Medical Services.

Outcome: Treatment uptake (proportion of individuals with HCV infection [HCV RNA positive] initiating DAA therapy)

Statistical analysis: Among people with HCV infection, the proportion of people who initiate DAA therapy will be calculated. Factors associated with DAA uptake will be assessed by logistic regression analyses. Sample Size: Given the assumed population distribution, we will enrol 120 participants with prevalent chronic HCV infection and 29 with incident HCV infection (with spontaneous clearance in 25% of incident cases). As such, 142 will be considered for DAA therapy. Assuming DAA uptake of 70% (based on LiveRLife [unpublished data]), the 95% Cl around this estimate is 62-78%. We will have 80% power to detect an odds ratio of 2.66 or greater (alpha=0.05) for a variable that is 50% prevalent (i.e. recent injecting drug use).

Response to DAA therapy among people with chronic HCV infection

Hypothesis: A community-based "test and treat" intervention integrating point-of-care HCV testing among people attending Aboriginal Medical Services will lead to HCV treatment response of >90%.

Outcome: Treatment response (SVR, defined as HCV RNA below the lower limit of quantitation 12 weeks following end of treatment).

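### The incidence rule can count a persisting, untreated infection as new, because one undetectable test opens risk time and no strain check is tied to the next positive

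*Protocol*

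**What the plan says.** Section 10 (Statistics, incidence of HCV infection) sets both ends of the observation. Entry: "Time at risk will commence at the date of first undetectable HCV RNA (or end of treatment"). The event is dated at the "midpoint between the dates of the last undetectable HCV RNA test (or end of treatment) and the first detectable HCV RNA test". Entry does not require a second undetectable test, and the event does not require a comparison of viral sequences. The rule is not limited to people who were RNA negative at enrolment or who were treated.

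Section 9.7 does use strain, but for a narrower group: "Among people with an end of treatment response, participants with HCV RNA recurrence (detectable HCV RNA) will be identified". Within that group, "HCV reinfection will be defined by the detection of infection with a strain distinct from the primary infecting strain". Section 9.1 adds a permissive line: "Data generated from the sequencing may also be used to distinguish relapse from reinfection".

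Untreated infected participants remain under observation. Section 6.1 says of those who decline treatment: "These participants may remain in the cohort and will be followed longitudinally". Section 5 allows the same for participants excluded from the community model, such as those with hepatitis B co-infection or prior DAA failure. Section 4.2 schedules six-monthly follow-up (FU1 to FU6) whatever the RNA or treatment status, and an RNA test and a dried blood spot are taken each time.

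**The concern.** The rule treats one undetectable result in an infected, untreated person as clearance. If that result is transient or a false negative, the next positive shows the infection the person already had, yet it enters the numerator as a transmission event. The interval between the two tests also enters the denominator, although the person was not at risk of a first or new infection.

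Sections 9.1 and 9.7 recognise that returning viraemia need not be a new infection, but the safeguard is written only for people with an end-of-treatment response. With only 29 incident infections expected, a few misclassified cases would visibly change the estimated rate, and the trial's incidence hypothesis is a fall of more than 50%.

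**Working it through.** **The plan's own figures (Section 10, uptake sample size).** Inputs are 120 prevalent and 29 incident infections, "with spontaneous clearance in 25% of incident cases", and 70% uptake.

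- Considered for treatment: 120 + 29 × (1 − 0.25) = 141.75, which rounds to the stated 142.
- 95% interval for 70% of 142: 0.70 ± 1.96 × √(0.70 × 0.30 / 142) = 62.5% to 77.5% (stated 62–78%).
- Implied overall rate with the synopsis's 715 person-years: 29 / 715 = 4.06 per 100 person-years.

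**People exposed to the rule.** Untreated prevalent infections: 120 × 0.30 = 36. Incident cases are left out. Their risk time ended at the first infection, and Section 10 does not describe re-entry.

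**Opportunities.** A false event needs an undetectable result followed by a positive, so only FU1 to FU5 can start one: five tests per person.

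**False events.** Let q be the chance per test of an isolated undetectable result in an infected person. The protocol gives no value, so q is an assumption. Allowing one event per person, expected false events = 36 × [1 − (1 − q)^5]. With 30% loss to follow-up, 36 becomes 36 × 0.70 = 25.2.

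| q (assumed) | False events | Relative to 29 | Rate per 100 PY | False events, 30% loss |
|---|---|---|---|---|
| 0.5% | 0.9 | +3% | 4.18 | 0.6 |
| 1% | 1.8 | +6% | 4.30 | 1.2 |
| 2% | 3.5 | +12% | 4.54 | 2.4 |
| 3% | 5.1 | +18% | 4.77 | 3.6 |
| 5% | 8.1 | +28% | 5.19 | 5.7 |

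The rate column is (29 + false events) / 715 × 100. The table assumes all 36 stay untreated through follow-up. Section 4.2 lets participants start treatment at any time, so the counts lean high.

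**Dates.** Visits fall at weeks 24, 48, 72, 96, 120 and 144. Under the midpoint rule, positives at FU2 to FU6 after a negative at the preceding visit are dated (24 + 48)/2 = 36, then 60, 84, 108 and 132 weeks of participant time.

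**Effect on the period comparison.** Take a true rate ratio of 0.50 with equal person-time, so that 29 events split 19.33 early and 9.67 late. Add 3.46 false events (q = 2%):

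- half early: (9.67 + 1.73) / (19.33 + 1.73) = 0.54
- 80% early: (9.67 + 0.69) / (19.33 + 2.77) = 0.47
- 80% late: (9.67 + 2.77) / (19.33 + 0.69) = 0.62

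The ratio is unchanged when two-thirds of the false events fall early, and it moves in opposite directions on either side of that share.

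**The case against.** Several counter-arguments carry weight.

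- **Intent.** Section 4.1 describes treated participants moving into the at-risk group after cure, which suggests that untreated people were not meant to enter. Section 10 does not carry that restriction, so the gap in the rule remains.
- **Sequencing is planned anyway.** Section 9.1 says that dried blood spots serve the endpoint analysis and that the viral genome will be sequenced, without limiting this to treated people. It would be wrong to infer that no data will exist to check these cases. But nothing in Section 9.1 makes the result part of the incidence definition.
- **A matter for the SAP.** Adjudication detail often belongs there. Here, however, the protocol itself fixes the entry and event rules, and following them as written gives the misclassification.
- **Frequency.** Most of the exposed infections are described as chronic, so transient control typical of acute infection may be rare among them. This stands: q could be at or below the bottom of the range.
- **True clearance.** After real spontaneous clearance, a later positive is a real infection. This stands, and spontaneous clearers should not be counted as a source of false events.

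A reader might infer that, because a false event needs three visits, such events gather in the later period and mask a fall in incidence. The documents do not support this. The midpoint rule dates the earliest at week 36, not at the week 48 visit that detects it. The initial and later periods are not defined, and Section 4.1 keeps recruitment open throughout, so participant weeks do not map onto periods.

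**Conclusion.** The point holds as a badly fixed definition for a secondary endpoint. As written, Section 10 can count a persisting untreated infection as incident, and the strain test in Section 9.7 does not reach it.

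The size is unknown. It is about 1 to 8 false events against 29 expected for an assumed 0.5% to 5% per test, about 2 to 5 at 1% to 3%, and about 0.6 to 5.7 over the full range with 30% loss to follow-up. These figures rest on 36 people staying untreated, five eligible visits each, and a per-test rate that the protocol does not supply. The overall rate would be overstated if any such events occur. Whether the period rate ratio moves up or down is not established. Prevalence, the primary endpoint, does not depend on this rule.

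**What to change.** Amend Sections 9.7 and 10 together.

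1. In Section 9.7, extend the sequence comparison to any reappearance of HCV RNA in a participant with an earlier RNA-positive dried blood spot, whether treated or not.
2. In Section 10, state that a same-strain reappearance is not an incident infection.
3. Where sequencing fails, count the event only if clearance had been confirmed by two consecutive undetectable scheduled tests, with risk time starting at the second. Starting at the first would credit about 24 weeks in which, by construction, no event could occur, and would bias the rate downward.
4. Add a sensitivity analysis limited to people RNA negative at enrolment plus treated participants.

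The cost is protocol wording and a few additional sequences from spots already collected at screening and follow-up. Some person-time is lost under the confirmation rule, and a true reinfection with the same strain would be missed.

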4.2 Visit Schedule

All participants will complete a screening visit as outlined below and in the Schedule of Assessments.

Those participants who are HCV RNA positive will be offered DAA therapy. Participants who decide to initiate DAA treatment will have on-treatment and post-treatment assessments as outlined in the Schedule of Assessments and described in Section 6.0. The treatment regimen of eight weeks glecaprevir/pibrentasvir or 12 weeks sofosbuvir/velpatasvir will be prescribed via the PBS S85. Participants who are HCV RNA positive may commence DAA treatment at any time during the study.

Following enrolment into the SCALE-C Cohort, regardless of HCV RNA or DAA treatment initiation, a followup visit will be conducted every 6 months for the duration of the study (up to three years; FU1–FU6).

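### DAA uptake is planned as an ever-started proportion with logistic regression although people have unequal time in which to start, and its denominator is not the one used for sizing

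*Protocol*

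**What the plan says.** The uptake part of protocol Section 10 gives the outcome as the "proportion of individuals with HCV infection [HCV RNA positive] initiating" DAA therapy. The estimator is fixed: "Among people with HCV infection, the proportion of people who initiate DAA therapy will be calculated". So is the model: "Factors associated with DAA uptake will be assessed by logistic regression analyses". Neither this text nor the endpoint lists in the synopsis and Section 10 attach a time period to uptake.

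The design sections determine how long each person has to start:

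- Section 4.1: "Recruitment into the SCALE-C cohort will remain open throughout the study period".
- Section 4.2: "Participants who are HCV RNA positive may commence DAA treatment at any time during the study".
- Section 4.2: six-monthly visits run "for the duration of the study (up to three years; FU1–FU6".
- Section 3.2: an RNA-positive result at follow-up qualifies for treatment as well as one at screening.

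The sizing for uptake combines 120 participants who have prevalent infection with "29 with incident HCV infection (with spontaneous clearance in 25% of incident cases", and arrives at 142 to be considered for treatment. It assumes 70% uptake, with a 95% interval of 62-78% and 80% power for an odds ratio of 2.66.

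**The concern.** A person found RNA positive at the first screening session may have three years in which to start treatment. A person who enrols late, or who first tests positive near the last visit, may have only weeks. A crude proportion counts both as fully observed, and so does a logistic model. The same section uses person-time for incidence and reinfection, so the plan recognises unequal observation there but not for uptake.

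Two things are at stake. First, the headline figure depends on the accrual pattern as well as on acceptance of treatment, and it cannot show how quickly people start, although prompt initiation is a listed component of the intervention (Section 4.1). Second, any factor that goes with late detection can appear to lower uptake. Incident versus prevalent infection is the clearest example, because incident infections are by construction found after baseline.

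A smaller matter is that the outcome keeps every RNA-positive individual, while the sizing first removes those expected to clear without treatment.

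**Working it through.** **1. The plan's own figures.** Inputs from Section 10: 120 prevalent, 29 incident, 25% clearance, 70% uptake.

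- Considered for treatment: 120 + 29 × 0.75 = 141.75, rounded to 142.
- Wald interval: 0.70 ± 1.96 × √(0.70 × 0.30 / 142) = 0.70 ± 0.075, or 62.5% to 77.5%, printed as 62-78%.
- Odds ratio 2.66, 71 v 71, two-sided 0.05 (sides are not stated), 70% falling to 46.7%: power 0.795 (Wald on the log odds ratio) to 0.810 (two proportions).

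All three reproduce.

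**2. Denominator.** The outcome as worded keeps 120 + 29 = 149 people. If 70% of the 142 start, that is 0.70 × 142 = 99.4, and 99.4 / 149 = 66.7% against 70%: about 3 points. This is an upper bound. With six-monthly RNA tests some infections clear before they are ever detected, and some people start treatment before they would have cleared.

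**3. Unequal observation.** The protocol gives no distribution of time to initiation, so this step rests on assumptions: eventual uptake 70%, half of starters (35%) on day 0, and the rest with exponential delay of mean m weeks. With observation time T,

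observed uptake = 0.35 + 0.35 × [1 − mean of exp(−T/m)].

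- Entry uniform over 144 weeks, so T is uniform on 0 to 144: mean of exp(−T/m) = (m/144) × [1 − exp(−144/m)].
- T uniform on 104 to 156 weeks (2 to 3 years, mean 2.5): mean of exp(−T/m) = (m/52) × [exp(−104/m) − exp(−156/m)]. The mean matches the synopsis: 715 / 286 = 2.5 years each, if all 286 contribute.

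| Mean delay m | T uniform 0-144 weeks | T uniform 104-156 weeks |
|---|---|---|
| 13 weeks | 66.8% | 70.0% |
| 26 weeks | 63.7% | 69.7% |
| 52 weeks | 58.2% | 67.0% |

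Only the 58.2% lies outside the stated 62-78%.

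**4. Apparent association with late detection.** Take the same treatment behaviour for two people, one with 144 weeks left and one first positive with 24 weeks left. The probability of being counted as a starter is 0.35 + 0.35 × [1 − exp(−T/m)].

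| m | T = 144 | T = 24 |
|---|---|---|
| 13 weeks | 70.0% | 64.5% |
| 26 weeks | 69.9% | 56.1% |
| 52 weeks | 67.8% | 47.9% |

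The gap within each row comes from observation time alone.

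**5. A second set of assumptions.** With a three-year study, 40% starting on the day and a rate of 0.5 per year afterwards, uptake is 1 − 0.6 × exp(−0.25) = 53% at 6 months and 1 − 0.6 × exp(−0.5) = 64% at 12 months. With uniform entry over A years, the ever-started proportion is 1 − 0.6 × [exp(−0.5(3 − A)) − exp(−1.5)] / (0.5A): 83%, 77% and 69% for A = 1, 2 and 3. The 6- and 12-month figures do not depend on accrual, whereas the ever-started figure does.

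**The case against.** Ever-started uptake is a legitimate step in a care cascade, and time windows or adjustment for enrolment date are often left to an SAP, which is not shown here. The first half of this stands. A reader might infer that the planned outcome does not measure uptake at all, but the text does not support that: it measures uptake by study end, and lacks only timeliness and equal observation. The second half is weaker, because the protocol itself names the crude proportion and the logistic model.

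The overall bias may also be small. If average observation is near the 2.5 years implied by the synopsis, the loss is at most about 3 points in the scenarios tried, and incident infections are only 29 of 149. This stands for the headline figure. It does not remove the problem for comparisons of incident with prevalent infection.

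On the denominator, the reference to 142 people considered for treatment suggests the intended population. That is a fair reading, but the outcome definition does not say so.

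A reader might also infer that the sizing counts infections while the outcome counts persons. The sizing sentence speaks of participants and nowhere says that the 29 include reinfections among the 120, so the documents do not support this. Reinfection also has its own objective and person-time analysis.

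**Conclusion.** The point holds for a secondary endpoint. The protocol fixes an uncensored proportion and a logistic model for an outcome whose observation time differs between people by design. Late-detected infections can therefore show lower uptake through shorter follow-up alone. For the overall proportion, the shortfall from 70% eventual uptake runs from almost nothing to about 3 points if people are observed for 2 to 3 years, and from about 3 to 12 points if entry is spread evenly over 144 weeks. Delay distribution, eventual uptake and accrual pattern are all assumptions. The denominator mismatch is separate, certain as wording, and worth at most about 3 points. There is no arithmetic error in the 142, the interval or the odds ratio.

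**What to change.** In Section 10, define the uptake analysis as the cumulative incidence of DAA initiation, counted from the first RNA-positive result of each participant's first infection in the study. Report it on the same day and at one stated horizon. Twelve months is an example. A 24-week cut-off would fall on the FU1 visit, and starts would be classified by visit timing. For infections found at screening, day 365 lies at the closing edge of the FU2 window (336 + 30 = day 366), so nearly all starts at that visit count. The horizon is for analysis only and is not a rule on when to treat.

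Use an Aalen-Johansen estimator, censoring at loss or study end, with untreated clearance and death as competing events. Plain Kaplan-Meier would not estimate this quantity. Use cause-specific Cox regression for factors. Keep the ever-started proportion beside it, and use one denominator in the outcome and the sizing text. With all 149 kept and 66.7% expected, the Wald half-width is 1.96 × √(0.667 × 0.333 / 149) = 7.6 points, against 7.5 now, so precision hardly changes.

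The cost is modest. The first-dose date is already recorded (Section 5.1) and RNA tests are tied to dated visits. There is slightly more analysis, clearance dates are known only to within a visit interval, and the statement on the odds ratio of 2.66 must be restated or kept for the ever-started analysis.
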